### 9.1.1 **Solicited Adverse Events**

The term “reactogenicity” refers to solicited signs and symptoms (“solicited AEs”) occurring in the hours and days following a vaccination. Subjects will be assessed for reactogenicity, to be collected by the subjects/parent(s)/LAR(s) for 7 days following each vaccination (the day of vaccination and the following 6 days), using a subject diary (pDiary). Solicited AEs will be recorded in the pDiary for the periods Day 1 to Day 7 and Day 61 to Day 67, with the exception that subjects in the MenACWY group who will have solicited AEs recorded only for Day 1 to Day 7. Solicited AEs occurring within 30 minutes of vaccination on Day 1 and Day 61 will be recorded by the investigator on the eCRF and will not be included in the pDiary. The MenACWY group will only have solicited AEs recorded for Day 1 to Day 7 (including 30 minutes post-vaccination on Day 1).

#### Solicited local AEs

Solicited local (injection site) AEs for this study are pain, erythema, swelling, and induration. Solicited local AEs will be recorded according to the vaccine that was administered and the site of administration (e.g. upper or lower deltoid and the arm used for administration).

#### Solicited systemic AEs

Solicited systemic AEs for this study are fever (body temperature  $\geq 38.0^{\circ}\text{C}$ ), nausea, myalgia, arthralgia, headache, and fatigue. The preferred location for measuring temperature in this study is the axilla.

#### Other solicited AEs

The use of analgesics/antipyretics (preferably paracetamol) for either prophylactic or treatment purposes will also be recorded as other solicited events in the pDiary and summarized with the solicited AEs.

Note: Any solicited AE that meets any of the following criteria will be entered into subjects' source document and also as an AE on the eCRF:

- Solicited local or systemic AE that continues beyond day 7 after vaccination.
- Solicited local or systemic AE that leads to a visit to a healthcare provider (medically attended AE).
- Solicited local or systemic AE leading to the subject withdrawing from the study or the subject being withdrawn from the study by the investigator (AE leading to withdrawal).
- Solicited local or systemic AE that otherwise meets the definition of an SAE.

Solicited AE's will be summarized according to the defined severity grading scales in Table 8. Body temperature will be classified as  $<38^{\circ}\text{C}$  (no fever) and  $\geq 38^{\circ}\text{C}$  (fever), as well as by  $0.5^{\circ}\text{C}$  increments from  $36.0^{\circ}\text{C}$  up to  $\geq 40^{\circ}\text{C}$ .

Missing values for solicited AEs will be handled as described in Section 4.3.

**Table 8 Solicited Adverse Event Intensity Grades**

Adverse Event	Intensity grade	Parameter
Pain at injection site	0	None
	1	Mild: Any pain neither interfering with nor preventing normal every day activities
	2	Moderate: Painful when limb is moved and interferes with every day activities
	3	Severe: Significant pain at rest. Prevents normal every day activities
Erythema at injection site	0	None: $<25$ mm surface diameter
	1	Mild: $25\text{-}50$ mm surface diameter
Swelling at injection site	2	Moderate: $51\text{-}100$ mm surface diameter
Induration at injection site	3	Severe: $>100$ mm surface diameter

Fever 		Record temperature in °C
Nausea	0	None
	1	Mild: Nausea present but not interfering with oral intake
	2	Moderate: Nausea leading to decreased oral intake
	3	Severe: Nausea leading to minimal to no oral intake
Myalgia	0	None
	1	Mild: Myalgia present but does not interfere with activity
	2	Moderate: Myalgia that interferes with normal activity
	3	Severe: Myalgia that prevents normal activity
Arthralgia	0	None
	1	Mild: Arthralgia present but does not interfere with activity
	2	Moderate: Arthralgia that interferes with normal activity
	3	Severe: Arthralgia that prevents normal activity
Headache	0	None
	1	Mild: Headache present but does not interfere with activity
	2	Moderate: Headache that interferes with normal activity
	3	Severe: Headache that prevents normal activity
Fatigue	0	None
	1	Mild: Fatigue that does not interfere with activity
	2	Moderate: Fatigue that causes some interference with activity
	3	Severe: Fatigue that prevents daily activity

The preferred route for measuring and recording temperature in this study is the axilla. When there is no other alternative, the temperature may be recorded by another route. If the temperature is taken by another route (oral, rectal, or tympanic), the route should be documented. Fever is defined as a body temperature  $\geq 38^{\circ}\text{C}$ .

Note: Temperature will be recorded in the evening. If additional temperature measurements are to be performed at other times of the day, the highest temperature measured will be recorded in the eCRF.

A summary table containing the number and percentage of subjects showing the occurrence of any local or systemic AE will be presented by study group and visit (Visit 1, Visit 3 and Any visit, the MenACWY group will only be included in Visit 1 and Any visit).

Subjects with solicited AEs will be counted based on actual treatment received for each study group using the Solicited Safety Set. The following categories will be included in the summary table for solicited AE:

1. Subjects who experienced any solicited AE within 7 days of vaccination
2. Subjects who experienced any systemic solicited AE within 7 days of vaccination
3. Subjects who experienced any local solicited AE within 7 days of vaccination
4. Subjects who experienced any local solicited AE on upper left deltoid within 7 days of vaccination
5. Subjects who experienced any local solicited AE on lower left deltoid within 7 days of vaccination

6. Subjects who experienced any local solicited AE on upper right deltoid within 7 days of vaccination
7. Subjects who experienced any local solicited AE on lower right deltoid within 7 days of vaccination
8. Subjects who experienced any other solicited AE within 7 days of vaccination

Categories 1 - 8 will be repeated for the following time points:

- Within 30 minutes of vaccination
- Within 1-3 days of vaccination (excluding 30 minutes post-vaccination)
- Within 4-7 days of vaccination

The number and percentage of subjects experiencing each solicited AE will be presented for each symptom maximal severity (defined in Table 8) by study group, visit (Visit 1, Visit 3 and Any visit, with the MenACWY group only included for Visit 1 and Any visit), and time point (30 minutes post vaccination, days 1 to 3 excluding 30 minutes post vaccination, days 4-7, days 1-7 excluding 30 minutes post-vaccination). Local solicited AEs will also be presented by maximal severity and site of administration: upper or lower deltoid, left or right arm. Pain and fever will also be summarized by the use of antipyretics/analgesics for the prevention and/or treatment of pain/fever.

If a solicited AE occurs more than once for a subject within a time point, it will be counted in the summary only once, according to the maximal severity.

Solicited AEs will be listed and the use of antipyretics/analgesics will be highlighted.

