### **10.9.2. Analysis of local and systemic adverse events**

All solicited AEs will be summarized according to defined severity grading scales (see [Table 12](#)).

Frequencies and percentages of subjects experiencing each AE will be presented for each symptom severity. Summary tables showing the occurrence of any local or systemic AE overall and at each time point will also be presented. Local AEs will be assessed according to which vaccine was administered and the site of administration (e.g. upper or lower deltoid and the arm used for administration).

Post-vaccination solicited AEs reported from day 1 to day 7 will be summarized for the intervals days 1 to 3, days 4 to 7, and days 1 to 7 by maximal severity and by study group, excluding the 30-minute post-vaccination measurement, which will be summarized separately. In addition, solicited AEs ongoing after day 7 will be presented as unsolicited AEs.

Body temperature will be classified as  $<38^{\circ}\text{C}$  (no fever) and  $\geq 38^{\circ}\text{C}$  (fever), as well as by  $0.5^{\circ}\text{C}$  increments from  $36.0^{\circ}\text{C}$  up to  $\geq 40^{\circ}\text{C}$ .

Erythema, induration, and swelling will be categorized as none (<25 mm), 25 to 50 mm (mild), 51 to 100 mm (moderate), and >100 mm (severe local reactions). The severity of pain will be categorized as none, mild (transient with no limitation in normal daily activity), moderate (some limitation in normal daily activity), and severe (unable to perform normal daily activity).

If an AE occurs more than once for a subject, it will be counted in the summary only once, according to the maximal severity. Summary tables showing the occurrence of any local or systemic AEs overall will be presented.

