### Safety Endpoints

- Solicited local and systemic AEs in all study groups
  - Occurrence of solicited local and systemic AEs during the 7 days (including the day of vaccination) after each vaccination (Day 1 to Day 7 and Day 61 to Day 67, Day 1 to Day 7 only for subjects in the MenACWY group)
- Unsolicited AEs in all study groups
  - Occurrence of unsolicited AEs during the 30 days (including the day of vaccination) after each vaccination (Day 1 to Day 31 and Day 61 to Day 91, Day 1 to Day 31 only for subjects in the MenACWY group)
- SAEs, medically attended AEs, AEs leading to withdrawal, and AESIs, in all study groups from informed consent signature to Visit 4 (Day 91)

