### Missing Data

For safety analyses, subjects who missed reporting symptoms (solicited or unsolicited) or concomitant medications will be analyzed to determine the missing mechanism. For the analysis of solicited symptoms, implausible measurements will not be replaced but they will be excluded from the analyses. Missing values will not be imputed for solicited/unsolicited AEs or concomitant medications.

In order to minimize the effect of missing data, the study period will be divided into time intervals for the safety analyses. For unsolicited AEs, the study period will be divided into the following intervals: all unsolicited AEs reported from day 1 to day 31 after vaccination (day of vaccination = day 1, Visit 1 and Visit 3 will be assessed separately and combined), medically attended AEs reported during the entire study period, AEs leading to premature withdrawal from the study during the entire study period, SAEs reported during the entire study period and AESI reported during the study period for the Unsolicited Safety Set.

Concomitant medications will be assessed for the entire study period for the Overall Safety Set.

Solicited AE data will be analyzed by the following intervals: 30 minutes post-vaccination on day of vaccination, 1 – 3 days post-vaccination (including the day of vaccination as day 1, excluding 30 minutes post-vaccination), 4 days – 7 days post-vaccination, and 1 day - 7 days (including the day of vaccination as day 1, excluding 30 minutes post-vaccination). Intervals will be assessed for Visit 1 and Visit 3, separately and combined, for the Solicited Safety Set. Solicited local AEs will be considered separately by vaccine for study groups where two vaccinations are administered at each visit, and also separately by location

A subject will be classified as having missing data within the specified intervals as described below:

- Solicited AEs
  - Temperature will be regarded as missing if “Temperature taken” = “No” at every time point within the interval (on Post-vaccination Body Temperature eCRF page).
  - Pain will be regarded as missing if no intensity values are recorded for Vaccine A and Vaccine B separately at every time point within the interval (on Vaccine A/Vaccine B Solicited Local Adverse Event eCRF pages). An intensity value of ‘None’ is a valid value and will not be considered a missing value.

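### No per-symptom severity row covers the full 7-day solicited AE window: the only whole-week interval leaves out the first 30 minutes, and the rows as planned cannot be added to recover it

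*SAP*

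**What the plan says.** **Endpoint.** Protocol 10.2 and SAP 3.2.2 define it identically: "Occurrence of solicited local and systemic AEs during the 7 days (including the day of vaccination) after each vaccination". Neither removes the first 30 minutes.

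**Data sources.** SAP 9.1.1 states: "Solicited AEs occurring within 30 minutes of vaccination on Day 1 and Day 61 will be recorded by the investigator on the eCRF". The same sentence keeps these events out of the diary. Protocol 11.2 makes the diary the source document for solicited events only once the clinic observation period is over.

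**Per-symptom, maximal-severity table (SAP 9.1.1, after Table 8).** It has four time points. The first two are given as "time point (30 minutes post vaccination, days 1 to 3 excluding 30 minutes post vaccination" and the last two as "days 4-7, days 1-7 excluding 30 minutes post-vaccination". On repeated events the rule is: "If a solicited AE occurs more than once for a subject within a time point, it will be counted in the summary only once", at the maximal severity.

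**Interval definitions elsewhere.** SAP 4.3 (Missing Data) defines the whole-week interval as "1 day - 7 days (including the day of vaccination as day 1, excluding 30 minutes post-vaccination". Protocol 10.9.2 sets the days 1 to 7 summaries up the same way: "excluding the 30-minute post-vaccination measurement, which will be summarized separately".

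**Any-event table (SAP 9.1.1).** Its leading category is "Subjects who experienced any solicited AE within 7 days of vaccination", followed by similar 7-day categories for systemic and local events. None states an exclusion. The categories are then repeated for shorter time points, and the 1-to-3-day one does state the exclusion.

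**The concern.** Safety is a named secondary objective, and this is its first-listed endpoint. A reader who wants the 7-day frequency and worst grade of, say, nausea or erythema will go to the whole-week row of the per-symptom table. That row answers a slightly different question from the endpoint. A symptom seen by staff and gone before the diary starts is not counted in it. A symptom that was worst in the clinic and continued more mildly enters at the milder grade, because the maximum is taken within a time point and not across them.

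The any-event table raises a related question. Its 7-day categories read as if they cover the whole window, while the interval defined in SAP 4.3 does not. Two programmers could reasonably produce different counts. If the 30 minutes are included, a subject can count as having an event within 7 days yet appear under no symptom in the whole-week row.

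**Working it through.** No design figure in the plan (power, alpha, sample size) bears on this point, so there is no stated number to reproduce. The check compares the windows and then bounds the possible gap.

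**Step 1: windows side by side.**

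| Item | First 30 minutes | Rest of days 1–7 | By symptom and severity |
|---|---|---|---|
| Endpoint (Protocol 10.2, SAP 3.2.2) | in | in | not specified |
| Per-symptom row, 30 minutes | in | out | yes |
| Per-symptom row, whole week | out | in | yes |
| Any-event 7-day categories | not stated | in | no |
| 30-day preferred-term summary (SAP 9.1.2) | no exclusion stated | in, but the window is 30 days | by term, no grade, not split by visit |

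No line that reports by symptom and severity is in for both windows.

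**Step 2: what the two per-symptom rows tell the reader.** For one symptom, visit and group of N subjects, let A be the number with it at the 30-minute time point and B the number in the whole-week row. The endpoint count U is the size of the union:

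max(A, B) ≤ U ≤ min(N, A + B)

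The shortfall is U − B, the subjects with the symptom in the first 30 minutes only. It is never negative and never exceeds A. With N = 100 (the planned approximate group size) and assumed counts:

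| A | B (shown) | U (endpoint) |
|---|---|---|
| 5 | 20 | 20 to 25 |
| 10 | 20 | 20 to 30 |
| 5 | 60 | 60 to 65 |

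The overlap is not reported, so U cannot be recovered from the table. By the same argument, maximal severity over the full window is equal to or higher than the grade in the whole-week row, and it can differ only for subjects counted in A.

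**Step 3: how often the gap would be non-zero.** If a share q of subjects has a symptom in the first 30 minutes only, the expected number left out of the whole-week row is 100q per group, and the chance of at least one is 1 − (1 − q)^100. The documents give no value for q, so these are assumptions:

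| q | expected omitted per 100 | chance of at least one |
|---|---|---|
| 0.1% | 0.1 | 9.5% |
| 0.5% | 0.5 | 39.4% |
| 1% | 1 | 63.4% |
| 2% | 2 | 86.7% |
| 5% | 5 | 99.4% |

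**Step 4: scale.** For an assumed true 7-day rate of 10% and q between 1% and 3%, the row would show 9% down to 7%. The standard error of a 10% rate at n = 100 is √(0.1 × 0.9 / 100) = 3.0 points, so the gap is at most about one standard error even under these assumptions.

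**The case against.** The separation is deliberate. The protocol prespecifies it, the SAP carries it out, and the two data streams differ in kind: staff observation on the eCRF against self-report in a diary. Keeping them apart is defensible. The endpoint wording also does not say that it applies symptom by symptom, and the any, systemic and local 7-day categories fit it well if they include the 30-minute data. The intervals are labelled, the same rule applies to every group, all analyses are descriptive, and a reaction still present after 30 minutes can enter the whole-week row through the diary.

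Most of this stands. It rules out an inference that a reader might draw from the whole-week row alone: that immediate reactions are missing from the safety reporting, or that the tables contradict each other. The 30-minute time point reports them by symptom and maximal severity, solicited events are listed, and the 30-day preferred-term summary states no exclusion. Differently labelled windows giving different counts is not a contradiction.

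Three things remain. Prespecifying an interval does not make it the endpoint window. Showing two overlapping rows does not let a reader rebuild their union. And whether the any-event categories fit the endpoint depends on a window that the SAP leaves unclear.

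**Conclusion.** The point holds as a mismatch between the endpoint window and the per-symptom severity summary. The whole-week row can only equal or understate the 7-day count and the maximal severity, with the count short by at most the 30-minute count for that symptom. The size is unknown, because the documents give no 30-minute rates; the percentages in the working are illustrations only. For common symptoms such as injection-site pain the effect on occurrence is probably small, since most subjects who have pain in the clinic would also be expected to report it in the diary; the grade could still shift.

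A claim that the reported rates will be biased by a particular amount would go beyond the documents. No decision rule rests on this row, so the trial's conclusions are not threatened. The change is still worth making before the tables are programmed, because it uses data already collected and lets the first-listed safety endpoint be read directly from a table.

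**What to change.** - In SAP 4.3 and 9.1.1, and in Protocol 10.9.2 at the next amendment, add one per-symptom interval covering days 1 to 7 with the first 30 minutes included. Count a subject if the symptom appears in either the eCRF assessment or the diary, and take maximal severity over both. Label it as the endpoint row.
- Keep the 30-minute interval and the whole-week interval without it as descriptive rows, as already prespecified.
- State in SAP 9.1.1 that the any, systemic, local and by-site 7-day categories use the same full window.

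The cost is a few lines of SAP text and one more interval in tables already planned; no new data are needed. The downside is that the endpoint row mixes staff-recorded and diary-recorded observations, which a footnote can state. If the sponsor prefers not to combine the sources, the minimum is to say in the endpoint text that the first 30 minutes are reported separately, and to fix the window of the any-event categories accordingly.

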### **9.1.2 Unsolicited Adverse Events**

An unsolicited AE is an AE that was not solicited using a pDiary and that was spontaneously communicated by a subject/parent(s)/LAR(s) who has signed the informed consent or a solicited local or systemic that meets the criteria described in Section 9.1.1. Solicited AEs lasting more than 7 days after vaccination (including the day of vaccination) are also recorded as AEs.

The original verbatim terms used by investigators to identify AEs in the Adverse Events page of the eCRF will be mapped to preferred terms (PT) using MedDRA version 20.1 or higher. The AEs will then be grouped by MedDRA preferred terms according to system organ class (SOC).

Unsolicited AE summaries will be based on the Unsolicited Safety Set.

The following summaries will present the number and percentage of subjects reporting each AE and will be presented by SOC and PT for each study group, grouped by three time points: 30 days post-vaccination at any visit, 30 days post-vaccination at Visit 1 and 30 days post vaccination at Visit 3. Note that the MenACWY group will not be included in the 30 days post vaccination at Visit 3 summary):

- Any unsolicited AE
- Unsolicited AEs that are possibly or probably related to vaccine(s) - (Relationship to study treatment = Yes)
- Severity of unsolicited AE

Additional summaries will present the number and percentage of subjects reporting AEs in the following categories and will be presented by SOC and PT for each study group from Day1 through till end of study for the Overall Safety Set:

- AEs leading to withdrawal from the study
- AEs leading to withdrawal from the study vaccine
- AEs leading to a medically attended visit
- AEs leading to death
- SAEs
- SAEs that are possibly or probably related to vaccine(s)
- SAEs leading to death
- SAEs that are possibly or probably related to vaccines(s) and leading to death

Listings will be presented for Any AEs, AEs that are possibly or probably related to vaccine(s), AEs leading to withdrawal from the study, AEs leading to withdrawal from the study vaccine, AEs leading to medically attended visit, AEs leading to death, SAEs, SAEs that are possibly or probably related to vaccine(s), SAEs leading to death, SAEs that are possibly or probably related to vaccine(s)

and leading to death. AEs that were reported as occurring prior to a subject receiving any study vaccine will only be included on the Any AEs listing.

In addition, a summary will be provided of the number and percentage of subjects with each solicited and unsolicited AE and occurrence (number of events) of each solicited and unsolicited AE, classified by system organ class and preferred term within 30 days post-vaccination after any visit, excluding SAEs, for the Overall Safety Set, for each study group.

Missing data will be handled as described in Section 4.3

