**Table 2 Treatment Labels**

Treatment Number	Treatment Label
P	MenABCWY
P	rMenBOMV+ACWY_S 
P	rMenBOMV+ACWY_D 
P	rMenBOMV
P	MenACWY

S = same arm approximately 2.5cm apart, D= different arms

Categorical data will be described using the subject count and percentage in each category. A row denoted ‘Missing’ will be displayed to account for missing values categorical summaries. The ‘Missing’ row will only be displayed if at least one study group has a non-zero count for this category. Note percentages will not be displayed in the ‘Missing’ row, to draw attention to the percentages for the non-missing categories. Unless specified otherwise, percentages will be based on the number of subjects in each study group within the analysis population. Percentages will not be displayed if the count for a study group is zero, in order to draw attention to the percentages for non-zero counts. Percentages will be displayed using one decimal place.

Continuous data will be described using descriptive statistics (i.e. n, mean, standard deviation, minimum and maximum). For the summary statistics of all numerical variables unless otherwise specified, minimum and maximum will be displayed to the same level of precision as reported. Mean will be displayed to one level of precision greater than the data collected. Standard deviation/standard error will be displayed to two levels of precision greater than the data collected. P-values will be rounded to three decimal places. If a p-value is less than 0.001 it will be reported as “<0.001” If a p-value is greater than 0.999 it will be reported as “>0.999”.

If statistical analysis cannot be performed for a particular serogroup or study group, then these should be displayed as “NC.” (not calculated). Confidence intervals that cannot be calculated should be displayed as “(NC.)”.

Data will be displayed in all listings sorted by study group. Subjects will be identified in the listings by the subject identification number.

Serogroups should be displayed in the order in Table 3. If the combined B serogroups are to be presented in a table or listing, this group should be displayed last.

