  - Erythema, swelling and induration will be regarded as missing if no measurements in mm are recorded for Vaccine A and Vaccine B separately at every time point within the interval (on Vaccine A/Vaccine B Solicited Local Adverse Event eCRF pages).
  - Nausea, myalgia, arthralgia, headache and fatigue will be regarded as missing if no intensity values are recorded at every time point within the interval (on Solicited General Adverse Events eCRF page). An intensity value of ‘None’ is a valid value and will not be considered a missing value.
- Unsolicited AEs
  - Non serious AEs will be regarded as missing if no AEs are recorded during the interval and there is no response to “Did the subject experience any non-serious adverse events during the study?” (Non Serious Adverse Event YN eCRF page).
    - Medically attended AEs will be regarded as missing if, in addition to the missing criteria for non-serious AEs, there is no response to “Medically attended visit” (Non Serious Adverse Events eCRF page).

- AEs leading to withdrawal from the study will be regarded as missing if, in addition to the missing criteria for non-serious AEs, there is no response to “Did the subject withdraw from the study as a result of AE?” (Non Serious Adverse Events eCRF page).
- Serious AEs will be regarded as missing if no SAEs are recorded during the interval and there is no response to “Did the subject experience a serious adverse event or a non-serious AESI during the study?” (Serious/Expedited Event YN eCRF page), or “Did the subject experience a serious adverse event or a non-serious AESI during the study?” = “Yes” and there is no response to “Serious” (Serious/Expedited Event eCRF page).
- AESI will be regarded as missing if there is no response to “Did the subject experience any arthritis/arthralgia (joint pain) events during the study?” (Arthritis/Arthralgia (Joint Pain) Events YN eCRF page).
- Concomitant medications will be regarded as missing if no concomitant medications are recorded on the Concomitant Medications eCRF page, and there is no response to “Were any medications taken?” on the Concomitant Medications YN eCRF page.

The following algorithm will be applied to each interval:

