#### **4.4.2 All Exposed Set**

All subjects in the All Enrolled Set who receive any study vaccination.

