#### **Unsolicited Safety Set (unsolicited adverse events)**

- All subjects in the All Exposed Set who attended at least 1 visit or had at least 1 safety call or at least 1 follow-up event (such as withdrawal from the study) after receiving any study vaccination.

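### By the SAP's default denominator, unsolicited AE percentages after the second vaccination count subjects who never received dose 2 as event-free

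*SAP*

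**What the plan says.** - **Set used.** SAP 9.1.2: "Unsolicited AE summaries will be based on the Unsolicited Safety Set". No separate set is named for each time point.
- **Time points.** Besides any visit, the same section asks for "30 days post-vaccination at Visit 1 and 30 days post vaccination at Visit 3". Three summaries are affected: any unsolicited AE, related AEs, and AEs by severity.
- **Who is in the set.** SAP 4.4.3: "All subjects in the All Exposed Set who attended at least 1 visit or had at least 1 safety call", or one follow-up event, after any study vaccination. The parent set in SAP 4.4.2 is "All subjects in the All Enrolled Set who receive any study vaccination". Dose 1 alone is enough.
- **Default denominator.** SAP 4, below Table 2, lets specific text override it, but otherwise "percentages will be based on the number of subjects in each study group within the analysis population".
- **Only exclusion named for the Visit 3 table.** SAP 9.1.2: "Note that the MenACWY group will not be included in the 30 days post vaccination at Visit 3 summary". Subjects of the other four groups who missed dose 2 are not mentioned.
- **Missing data.** SAP 4.3: "Non serious AEs will be regarded as missing if no AEs are recorded during the interval" and, in addition, the yes/no question on non-serious AEs, which covers the whole study, is unanswered.

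**The concern.** A subject who stops after dose 1 has no period after dose 2. In a table of events after dose 2, that subject adds one to the denominator and can add nothing to the numerator. This is a lack of exposure rather than an absence of events. The SAP accepts the principle when it drops the single-dose MenACWY group from the Visit 3 table, but it does not carry it through to individuals in the two-dose groups.

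The safety endpoint in Protocol 10.2 is defined after each vaccination, with its own Day 61 to Day 91 window, so the dose-2 percentage is a planned result. Missing dose 2 may also be informative. Protocol 6.5 bars further vaccination after certain events, Protocol 9.2.2 lists AEs among the reasons for stopping vaccine, and Protocol 9.2 does not replace withdrawn subjects. If reactions to dose 1 led more subjects in one group to stop, that group's dose-2 percentages would be pulled down further than the others'.

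**Working it through.** **Step 1. The plan's own safety figure.** The only safety probability in the documents is 99.3% for seeing an AE of rate 1/100 among 500 subjects (SAP 4.1). 1 − 0.99^500 = 0.9934, which agrees. The documents give no AE rate after dose 2 and no share of subjects expected to miss it.

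**Step 2. Follow a dose-1-only subject through the rules.** Take a subject in a two-dose group who is vaccinated at Visit 1, attends Visit 2 and gets no vaccine at Visit 3.
- All Exposed Set: yes, one vaccination suffices.
- Unsolicited Safety Set: yes, Visit 2 is a later contact.
- Removed from the Visit 3 table by SAP 9.1.2: no, only MenACWY is.
- Removed by SAP 4.3: not if the study-level AE question has an answer, because the record is then not missing. Even if it is unanswered, the algorithm states a smaller denominator only when at least 20% of subjects lack data and Fisher's exact p is below 0.05 between groups.
- Removed by the per-dose wording in Protocol 10.6: no, that sentence concerns solicited symptoms.

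The subject therefore stays in the denominator.

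**Step 3. Size.** Let r be the true rate among dose-2 recipients and d the share of the group's set without dose 2. Then:

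shown rate = r × (1 − d), and understatement = r × d.

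With 100 subjects (the planned group size), d = 10% and r = 20%, 90 subjects receive dose 2 and 18 have an event. The SAP default gives 18/100 = 18.0%; dose-2 recipients give 18/90 = 20.0%.

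d is an assumption throughout:

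| d | r = 10% | r = 20% | r = 30% |
|---|---|---|---|
| 2% | 9.8% | 19.6% | 29.4% |
| 5% | 9.5% | 19.0% | 28.5% |
| 10% | 9.0% | 18.0% | 27.0% |
| 15% | 8.5% | 17.0% | 25.5% |

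**Step 4. Between groups.** If d is equal, every group shrinks by the same factor and their ratio is unchanged. If d differs, equal true rates separate. With r = 20% and d of 2% versus 10%, the table shows 0.20 × 0.98 = 19.6% and 0.20 × 0.90 = 18.0%, an artefact of 1.6 points.

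**Step 5. Against sampling error.** At r = 20% and n = 100, the standard error of one percentage is √(0.20 × 0.80/100) = 4.0 points, and of a difference √2 × 4.0 = 5.7 points.

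**The case against.** The sentence on the Unsolicited Safety Set names a set, not a denominator for each time point. The denominator comes from a general default that gives way to specific text. SAP 4.3 counts the day of vaccination as day 1 of the interval and assesses Visits 1 and 3 separately, so someone not vaccinated at Visit 3 has no interval. A programmer could sensibly restrict the table on that ground. This makes the intention arguable, but nothing in 9.1.2 overrides the default, and the one exclusion it states is of a whole group.

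The practical weight is also limited. Protocol 10.10 makes all analyses descriptive, and the SAP plans no between-group test of AE rates. SAP 7.2.1 tabulates by visit who did not receive all vaccinations and why, and SAP 9.1.2 summarizes and lists AEs leading to withdrawal from study vaccine. The attrition would be visible, and a reader could roughly re-divide. The correction would be approximate, because the exposure table uses the All Enrolled Set and groups partial vaccinations with missed ones. These arguments stand as limits on importance; they do not make the denominator right.

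A reader might infer that the plan will produce materially biased comparisons, with the more reactogenic group looking safer after dose 2. The documents do not support that. A split such as 3% versus 15% without dose 2 would turn equal rates of 20% into 19.4% and 17.0%, but nothing in the protocol or SAP points to so large an imbalance between randomized groups in a study of about 91 days in healthy subjects. Even that 2.4-point gap is under half of the 5.7-point standard error.

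**Conclusion.** The point holds as a defect in the stated denominator. It follows from three provisions read together: the set named in SAP 9.1.2, its entry rule in SAP 4.4.2 and 4.4.3, and the default in SAP 4. Subjects without dose 2 count as event-free after dose 2, and no other rule reliably removes them. The relative understatement equals the share of the set without dose 2. For a true 20% and an assumed 2% to 15%, it is 0.4 to 3.0 percentage points.

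The effect is probably small and confined to descriptive tables. It deserves correction because its direction is known, because it could differ between groups if missed second doses do, and because the remedy is simple. The point does not extend to the Visit 1 or any-visit summaries, nor to the solicited AE tables. Nor do the documents show that second doses will be missed unequally or because of reactions to dose 1; those are the circumstances in which the effect would matter most.

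**What to change.** Add to SAP 9.1.2: for the post-Visit 3 time point of the three unsolicited AE summaries (any, related, by severity), the denominator is the subjects of the Unsolicited Safety Set who received any study vaccine at Visit 3 and had at least one visit, safety call or follow-up event afterwards.

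The follow-up condition is needed because a subject lost straight after dose 2 would otherwise still be counted as event-free. Receipt of any study vaccine settles how to count subjects of the two-injection groups who received only one of the two at that visit. Keep the full set for the Visit 1 and any-visit summaries, and print the resulting number of subjects in each Visit 3 column.

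The cost is one sentence and one denominator flag. Vaccine administration by visit and later contacts are already recorded, so no new data are needed.
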